## **5.4 Treatment Assignment Procedures**

### **5.4.1 Subject Identification Procedure**

All subjects who are screened for the study (i.e., LAR signing the informed consent) will be assigned a subject identification number and will be included on the Screening and Enrollment Log. Subject identification numbers will be assigned sequentially starting with: ECCMN-001. If a subject does not meet eligibility criteria, that subject is considered a screen failure.

### **5.4.2 Reasons for Withdrawal**

Subjects may be voluntarily withdrawn by their LAR from the study for any reason at any time. A subject may also be withdrawn from the study for one of the following reasons:

- The Investigator deems it is in the subject's best interest, or in the interest of study data integrity, to discontinue the subject from the study for clinical, safety, non-adherence or other reason.
- The subject is lost to follow up.
- New information becomes available that makes further participation unsafe.
- The study is terminated by the Investigator or Sponsor.

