### **5.4.3 Handling of Withdrawals**

The LAR(s) of an infant or young child will be informed that they have the right to discontinue their child's study participation at any time without prejudice. Although the LAR(s) are not obligated to state the reason for withdrawal, every attempt should be made to establish if the reason for discontinuation is due to the study product or an AE. LAR(s) who withdraw their child for any reason should be asked to complete an Early Termination Visit.

Ongoing AEs or reactogenicity should be followed to resolution if the LAR is agreeable to continued phone contact by the study staff. Subjects who are withdrawn from the study

for any reason will not be replaced, unless there are fewer than 4 subjects who have reached Day 8 for any given age group.

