#### **5.4.4 Termination of Study**

The study may be terminated at any time by the Sponsor for clinical, safety or administrative reasons.

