### **9.2.3 Serious Adverse Events**

SAEs will be collected from Day 1 (after placebo microneedle administration) through the end of study participation. Any suspected SAE that occurs outside of the protocol-specified follow-up period and considered to be caused by the study placebo microneedle must be reported.

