## **12.5 Study Discontinuation**

If the study is discontinued, enrolled subjects will continue to be followed for safety assessments as specified in the protocol.

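### Sections 5.4.2 and 12.5 disagree on follow-up after study termination, and after any 5.4.2 withdrawal nothing actively seeks new events to Day 27–38

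*Combined protocol and SAP*

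**What the plan says.** **Withdrawal.** Section 5.4.2 opens its list with "A subject may also be withdrawn from the study for one of the following reasons". The grounds include an investigator's decision "to discontinue the subject from the study for clinical, safety, non-adherence or other reason", the case where "New information becomes available that makes further participation unsafe", and "The study is terminated by the Investigator or Sponsor". Section 5.4.4 adds: "The study may be terminated at any time by the Sponsor for clinical, safety or administrative reasons".

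**Follow-up after the study stops.** Section 12.5: "If the study is discontinued, enrolled subjects will continue to be followed for safety assessments as specified in the protocol".

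**Follow-up after a child leaves.** Section 5.4.3 has LARs who withdraw their child asked to complete an early termination visit, and Section 7.7 describes a premature discontinuation visit if the LAR agrees. Beyond that, 5.4.3 says: "Ongoing AEs or reactogenicity should be followed to resolution if the LAR is agreeable to continued phone contact by the study staff". Withdrawn children are not replaced unless an age group has fewer than 4 children who have reached Day 8.

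**Collection period.** Section 9.2.1 collects unsolicited AEs and SAEs up to the Day 27–38 end-of-study contact. Section 9.2.3 words it differently: "SAEs will be collected from Day 1 (after placebo microneedle administration) through the end of study participation". It then requires reporting of a suspected SAE outside the follow-up period if it is considered caused by the patch.

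**Endpoints and analysis.** The primary patch-related SAE endpoint, and the secondary endpoints of Grade 3 patch-related unsolicited AEs and new-onset medical conditions (NOMC), all run from Day 1 to Day 27–38 (Section 3.2). Section 11.3 defines the safety population as every child who receives a patch, and reports numbers and percentages of subjects.

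**The concern.** Once a patch has been applied, the child is exposed, and the safety question is what happens up to the final call. Stopping further patches and stopping observation are separate decisions, but 5.4.2 speaks only of leaving the study. If the site treats a 5.4.2 withdrawal as the end of participation, 9.2.3 ends SAE collection at that point, and no other provision contacts the family to ask about new events.

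At stake is the completeness of the primary SAE window and of two secondary endpoints. Several of the listed grounds relate to safety, so the missing time could be informative: the children least observed might be those about whom there was most worry. With at most 25 children per cohort, a few incomplete windows can matter to how a zero count is read.

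**Working it through.** The plan states no figure for withdrawals or completeness of follow-up, so there is none to reproduce. The check is mainly a comparison of text.

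**1. Study termination.** Section 5.4.2 permits withdrawal from the study; 12.5 requires continued safety follow-up. Section 12.5 refers back to what the protocol specifies, and the protocol includes 5.4.2, so the text does not settle which governs.

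**2. Individual withdrawal.** Section 12.5 applies only if the study is discontinued. Section 9.4 keeps children in follow-up to Day 27–38, but only those barred from patches 2/3 by an ongoing event. Neither reaches a child withdrawn individually under 5.4.2. This is a gap, not a contradiction.

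**3. What remains after such a withdrawal.**
- One discontinuation visit, if the LAR agrees (7.7).
- Phone contact for events already ongoing (5.4.3). Sections 9.2.4 and 9.3.3 likewise follow events already identified.
- Reporting of later SAEs considered patch-caused (9.2.3), with no contact scheduled to find them.

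None of these actively looks for a new SAE, unsolicited AE or NOMC. Section 9.2.1 (to Day 27–38) and 9.2.3 (to end of participation) give the same end point for a child who completes, and different ones for a child who leaves.

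**4. Days lost per child.** Inputs: window end Day 27 to Day 38 (Section 3.2); visit days from Section 7. Days lost = window end − last contact day; share = days lost ÷ window end.

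| Last contact | Ends Day 27 | Ends Day 38 |
|---|---|---|
| Day 2 | 27 − 2 = 25 (93%) | 38 − 2 = 36 (95%) |
| Day 8 | 27 − 8 = 19 (70%) | 38 − 8 = 30 (79%) |
| Day 15 | 27 − 15 = 12 (44%) | 38 − 15 = 23 (61%) |

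**5. Weight of one child.** 1/25 = 4% of a full cohort. In Cohort 1 age groups at their maximum size (Table 1): 1/12 = 8%, 1/7 = 14%, 1/6 = 17%.

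**6. Illustration of lost detection.** Assumptions, none from the plan except where stated: 25 children; a 5% risk per child over the whole window (a rate that Section 11.2 uses for AEs; no SAE rate is given); constant hazard; k children last seen at day d = 8; window end e; no passive capture.

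P(at least one observed event) = 1 − 0.95^[(25 − k) + k·d/e]

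- k = 0: 1 − 0.95^25 = 72.3%.
- k = 1: exponent 24 + 8/27 = 24.30 gives 71.2%; exponent 24 + 8/38 = 24.21 gives 71.1%.
- k = 12 (the largest Cohort 1 age group): exponent 13 + 96/27 = 16.56 gives 57.2%; exponent 13 + 96/38 = 15.53 gives 54.9%.

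A single withdrawal barely changes detection. Truncating a whole age group would.

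**The case against.** The case on the other side is substantial.

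- **Section 5.4.2 is permissive and 12.5 is mandatory.** A site can satisfy both by continuing follow-up. This stands: truncation is allowed by the text, not required, and it would be wrong to say that the site has two instructions it cannot obey together.
- **The protocol's defined response to a safety signal is halting, not withdrawal.** Section 9.5 stops enrolment and patch application and withdraws nobody; 9.4 keeps barred children to Day 27–38. This also stands. A reader might infer that the SAE window is cut exactly when a signal appears, and the documents do not support that. The route that remains is a termination for safety under 5.4.4, or an individual 5.4.2 withdrawal.
- **Late patch-related SAEs must still be reported.** The primary SAE endpoint counts only patch-related SAEs, so this mitigation is relevant. It is passive, however, and does not cover unsolicited AEs or NOMC.
- **Withdrawal can prevent exposure.** A reader might think that it only ends observation because a patch is worn once and removed. Up to three patches are allowed, two of them at Day 8, so withdrawal before then can prevent further application. The point concerns only patches already applied.
- **The study is descriptive.** True, but a percentage of subjects over a stated window still depends on that window having been observed.

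**Conclusion.** The point holds in a limited form. On study termination, 5.4.2 and 12.5 need reconciling. For exposed children withdrawn individually, follow-up for new events to Day 27–38 is not provided for. A reader might take 12.5 as contradicting those individual withdrawals too; it does not, because it speaks only of discontinuing the study.

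Nor does the plan say that a withdrawn child is counted as event-free. Section 11.3 is silent on incomplete windows. Counting such a child in the denominator with no event is what a plain number-and-percentage table would do by default, but that is an inference.

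The size is per child: 19 to 30 days lost for a withdrawal at Day 8 with no further contact. The documents give neither a withdrawal rate nor an SAE rate, so no expected loss can be calculated, and the detection probabilities above are illustrations under stated assumptions. The correction is worth making because the primary safety window is affected and the remedy is cheap. It does not call the design into question.

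**What to change.** - **Sections 5.4.2, 5.4.3, 9.2.1, 9.2.3 and 12.5:** reconcile them so that they distinguish receiving no further patches from the end of data collection, and state which applies when a child leaves under 5.4.2 or the study is terminated. The grounds for withdrawal stay with the investigator and sponsor; the change concerns data collection only.
- **Section 5.4.3:** extend the optional phone contact, where the LAR agrees, from ongoing events to the already scheduled Day 27–38 call, asking about new SAEs, unsolicited AEs and NOMC, for every exposed child who leaves.
- **Section 11.3:** beside the event percentages, report the number of children with complete ascertainment to Day 27–38.

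The cost is protocol wording and one already planned call per withdrawn child. The LAR may refuse the call, so some windows will stay incomplete; the added count in 11.3 makes that visible.

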### **5.4.3 Handling of Withdrawals**

The LAR(s) of an infant or young child will be informed that they have the right to discontinue their child's study participation at any time without prejudice. Although the LAR(s) are not obligated to state the reason for withdrawal, every attempt should be made to establish if the reason for discontinuation is due to the study product or an AE. LAR(s) who withdraw their child for any reason should be asked to complete an Early Termination Visit.

Ongoing AEs or reactogenicity should be followed to resolution if the LAR is agreeable to continued phone contact by the study staff. Subjects who are withdrawn from the study

for any reason will not be replaced, unless there are fewer than 4 subjects who have reached Day 8 for any given age group.

#### **5.4.4 Termination of Study**

The study may be terminated at any time by the Sponsor for clinical, safety or administrative reasons.

## **6 STUDY INTERVENTION/INVESTIGATIONAL PRODUCT**

### **6.1 Study Product Description**

#### **6.1.1 Acquisition**

Microneedle patches will be provided by Micron Biomedical.

#### **6.1.2 Formulation, Packaging, and Labeling**

Microneedle patches will be manufactured by Micron Biomedical. Microneedle patches will be made of excipients that are expected to include trehalose, sorbitol, histidine, maltodextrin, sodium carboxymethylcellulose, polysorbate, xylitol, polyvinyl alcohol, and/or glycerol. The total mass of excipients delivered by placebo microneedle patch will be <1.5 mg. The microneedle patches used in the placebo study will be manufactured under low bioburden conditions and in compliance with cGMP requirements for Phase 1 clinical trials according to the *FDA's Guidance for Industry 2008: CGMP for Phase 1 Investigational Drugs*. The adhesive backing component is made from hypoallergenic material (commercial 3M medical tapes designed to adhere to skin).

#### **6.1.3 Product Storage and Stability**

Microneedle patches will be stored at room temperature (i.e. 20^0C - 25C).

### **6.2 Dosage, Preparation and Administration of Study Intervention/Investigational Product**

Microneedle patches will be administered topically by manual application to the skin. The sites of microneedle patch application will be cleaned with an alcohol swab and allowed to dry before the microneedle patch is applied. The microneedle patches will be packaged and provided as single patches.

### **6.3 Accountability Procedures for the Study Intervention/Investigational Product(s)**

The Principal Investigator is responsible for study investigational product accountability, reconciliation, and record maintenance. In accordance with all applicable regulatory requirements, the Principal Investigator or designated study center personnel must maintain accountability records throughout the study.

## 7 STUDY SCHEDULE

Procedures to be performed at each study visit are detailed below. Refer also to Appendix A: Study Schedule.

### 7.1 Visit 1: Enrollment/Application of Placebo Microneedle Patch, Day 1

The following assessments will be performed on the day of enrollment prior to administration of the placebo microneedle patch.

- Informed Consent obtained.
- The optional consent for the optional placebo microneedle patches 2/3 may be signed.
- Inclusion/Exclusion criteria review.
- Complete medical history via interview with LAR including vaccination history.
- Record medications administered within the past 30 days and any concomitant medications.
- Vital signs: temperature and pulse.
- Complete physical examination.
- Height and weight.
- Baseline acceptability questionnaire.

The following procedures will be performed after subject eligibility has been verified:

- Subject enrolled.
- A baseline photograph of the area of application may be obtained.
- Application of placebo microneedle patch to the skin by a trained study nurse. The microneedle patch will remain in place for up to 20 minutes. The patch will then be removed and the used patch will be saved.
- The memory aid, thermometer and ruler will be provided to the LAR and instructions will be provided.
- The site of the placebo microneedle patch removal will be assessed at least 15 minutes and 30 minutes post-placebo microneedle patch removal. Per investigator discretion, photographic documentation (refer to MOP) and dermatologic referrals may be obtained.
- Study personnel will assess and record all AE/SAEs that occur after enrollment.
- The acceptability questionnaire will be completed by the LAR.

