### 7.2 Visit 2: Day 2 (+1) Clinic Visit

The following assessments will be performed.

- Obtain interim medical history and note any changes since the last visit.
- Record concomitant medications.
- Symptom-directed physical examination, if needed.
- Vital signs: temperature and pulse.
- Examine placebo microneedle patch application site. Subjects with localized rash, scarring or evidence of infection at placebo microneedle patch application site are to be evaluated by a study investigator. Per investigator discretion, photographic documentation (refer to MOP) and dermatologic referrals may be obtained.
- Study personnel will review the memory aid information with the LAR and record all AE/SAEs.
- The follow-up acceptability questionnaire will be completed by the LAR.

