## **8 STUDY PROCEDURES/EVALUATIONS**

### **8.1 Clinical Evaluations**

#### **8.1.1 Medical History**

A complete medical history will be obtained by direct interview with the LAR. LAR(s) will be asked about any history in their infant or young child of significant medical disorders of the head, eyes, ears, nose, throat, mouth, cardiovascular system, respiratory system, gastrointestinal tract, liver, pancreas, kidney, urologic system, nervous system, blood and lymphatics, endocrine system, musculoskeletal system, skin and genit/ reproductive tract. A history of any allergies or hypersensitivities, cancer, immunodeficiency, and autoimmune diseases will be solicited. Interim medical history is also obtained at each clinic visit.

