### **8.1.5 Reactogenicity**

The LAR will be provided with a memory aid, thermometer and ruler and will be instructed to record the presence of solicited symptoms and oral temperature through the Day 8 (+2 days) (Day 15 +3 days in those having microneedle patches 2/3 placed).. If a symptom is still present at that time, the LAR will continue to follow that symptom until two days symptom-free. Memory aids will be reviewed and collected by study staff at follow-up visits.

Solicited local microneedle patch application site symptoms include:

- Pain
- Erythema
- Ecchymosis (bruising)
- Induration/swelling
- Pruritus (itching)
- Tenderness

Solicited systemic reactions include:

- Fever
- Irritability (fussiness) above baseline
- Lethargy (drowsiness)
- Decreased appetite
- Vomiting

The LAR will use the following grading scale for describing symptoms:

- Grade 0: Not present
- Grade 1: Mild (present but easily tolerated)
- Grade 2: Moderate (able to tolerate routine activity with effort)
- Grade 3: Severe (unable to continue routine activity)

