### **9.2.1 Adverse Events**

All AEs occurring while on study during the AE reporting period must be documented appropriately regardless of seriousness, severity, or causal relationship to study product administration. AEs will be recorded on the AE page of the CRF.

Solicited AEs will be collected from Day 1 (after placebo microneedle placement) through Day 8 following placebo microneedle administration (Day 15 in those receiving placebo microneedle patches 2/3). Unsolicited AEs and SAEs will be collected from Day 1 (after placebo microneedle placement) through the Day 27 – 38 end of study visit. AE details will be collected via interview with the subject LAR. Information to be collected includes event description, date of onset, severity and date of resolution/stabilization of the event. Severity and relationship to study product (either “related” or “unrelated”) must be assessed by the Investigator or sub-investigator. Signs and symptoms due to a single diagnosis will be reported as the diagnosis. For example, cough, pharyngitis, rhinitis would be reported as “upper respiratory infection”. If multiple signs/symptoms presenting simultaneously cannot be attributed to the same etiology, then each symptom should be reported separately.

Any medical condition present at the time the subject is screened, or occurring prior to placebo microneedle placement will not be considered an AE, but will be captured in the medical history form. If a preexisting condition worsens (changes in severity or quality, not consistent with the subject’s reported past history of the condition) at any time during the study, this change should be captured as an AE.

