## 14 SUPPLEMENTS/APPENDICES

### 14.1 Appendix A: Study Schedule

Visit #	1	2	3	4 &	5 &	Final*		
Procedures	D1	D2 +1	D8 +2	D9 +2	D15 +3	D27 - D38	Unscheduled Visit (If needed)	Premature Discontinuation
Signed Consent Form	X							
Inclusion/Exclusion Review	X							
Complete Medical History	X							
Concomitant Medications	X	X	X	X &	X &	X	X	X
Interim Medical History		X	X	X &	X &	X	X	X
Sign Optional Consent For Microneedle Patch 2/3	(X )		(X)					
Application of microneedle patch	X		X &					
Distribute memory aid, ruler & thermometer	X		X &					
Review memory aid		X	X	X &	X &	(X)	(X)	(X)
Physical Exam	Complete Physical Exam	X						
	Assessment of microneedle patch application site	X* *	X	X* *&	X &	X &	X	X
	Symptom-Directed Physical Exam		(X)	(X)	(X) &	(X) &	(X)	(X)
	Height and weight	X						
	Vital Signs ^	X	X	X	(X) &	(X) &	X	X
Photograph site of placebo microneedle patch	(X )	(X)	(X)	(X)	(X)	(X)	(X)	(X)
Assessment of Adverse Events and SAEs	X* *	X	X	(X) &	(X) &	X	X	X
Acceptability Questionnaire	X	X	X	(X) &	(X) &	X	X	X

\* The final study visit will be a telephone call at D27 – D38

\*\* Occurring 15 minutes and 30 minutes after microneedle patch removal.

& At Day 8 the LARs of subjects who no ongoing solicited or unsolicited general AE or local AEs will have the opportunity to decide to have second and third placebo microneedle patches placed at different body sites from the initial location. In those that elect to have a second/third placebo microneedle patch placed, they will return for clinic visits on Day 9 and Day 15.

^ Vital signs will include temperature and pulse.

(X) – As indicated/appropriate.

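### Visit 1 requires a pre-patch value for only one of the five solicited systemic symptoms, so the rules on pre-existing and worsening symptoms have no graded starting point for the other four

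*Combined protocol and SAP*

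**What the plan says.** Section 7.1 opens the Visit 1 procedures with "The following assessments will be performed on the day of enrollment prior to administration of the placebo microneedle patch". The items under it are consent, eligibility review, a medical and vaccination history from the LAR, medications, temperature and pulse, a full examination, height and weight, and a first acceptability questionnaire. Appendix A follows the same pattern; its footnote reads "Vital signs will include temperature and pulse". In the order of section 7.1, the memory aid is handed over after the patch application step.

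Section 8.1.5 solicits five systemic symptoms: fever, irritability, lethargy, decreased appetite and vomiting. Irritability is listed as "Irritability (fussiness) above baseline". On the LAR's scale, the lowest grade above zero begins "Grade 1: Mild (present but easily tolerated".

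Section 9.2.1 states: "Any medical condition present at the time the subject is screened, or occurring prior to placebo microneedle placement will not be considered an AE". The same sentence sends such a condition to the medical history form. The next rule begins "If a preexisting condition worsens (changes in severity or quality", and makes a departure from the reported past history an AE. On the content of that history, section 8.1.1 says "LAR(s) will be asked about any history in their infant or young child of significant medical disorders". The Day 2 list in section 7.2 includes "Obtain interim medical history and note any changes since the last visit". Section 11.3 bases its AE tables on treatment-emergent events and is descriptive throughout.

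**The concern.** The rules are sensible, but for four symptoms they compare the post-patch state with a pre-patch state that nobody is required to grade. A history directed at significant disorders need not record that an infant was a little drowsy or feeding poorly that morning. The LAR then scores what is present, whether new or not.

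This matters because there is no control arm, so each child's own starting state is the only comparator. Section 4 says that safety is measured by systemic as well as application-site reactogenicity. Errors can run both ways: a mild symptom already present may be listed as a reaction to patch 1, or a true worsening may be put down to how the child already was.

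**Working it through.** The plan gives no figure on this point, and the detection chances in section 11.2 do not bear on it. The check is a count, then a tracing of where the gap reaches, then an illustration of scale.

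**1. Count.** Symptoms from section 8.1.5, set against the pre-application list in 7.1 and the Day 1 column of Appendix A:

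| Solicited systemic symptom | Required pre-patch value | What else helps |
|---|---|---|
| Fever | Temperature | Exclusion of recent febrile illness (5.3, item 1) |
| Irritability | None | Solicited relative to baseline |
| Decreased appetite | None | The term implies a comparison with usual intake |
| Vomiting | None | A discrete event; date of onset is collected (9.2.1) |
| Lethargy | None | Neither a comparative term nor a discrete onset |

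With a required value: 1 of 5. Without: 5 − 1 = 4 of 5. The gap is widest for lethargy. It is narrower for the other three but not closed: a comparative term asks the LAR to compare with a state that was not recorded, and a date of onset alone does not separate before from after the patch on Day 1.

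**2. Where the gap reaches.**
- Primary reactogenicity endpoint (3.2.1): application-site only, so unaffected.
- Primary solicited safety endpoint (3.2.1): needs Grade 3 and a patch relationship. A starting grade could inform attribution of a Grade 3 systemic event, here and under the study halting rule in 9.5, but only marginally, because a child that unwell should not pass the good-health criterion.
- Descriptive systemic tables after patch 1: exposed, mainly at the mild end.
- Patches 2/3: the memory aid covers the preceding week, and 9.4 bars a child with any ongoing Grade 1 or higher general AE. The starting state is already controlled.

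**3. Scale, for illustration only.** One misfiled child in a cohort of 25 moves a percentage by 1/25 = 4.0 points. That is true of any single error in 25 children and says nothing about how often this one occurs.

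Let q be the assumed proportion of children with at least one of the four symptoms before the patch. The documents give no value for q. The expected number is 25q, and the chance of at least one such child is 1 − (1 − q)^25:

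| Assumed q | Expected in 25 | Chance of at least one |
|---|---|---|
| 2% | 0.02 × 25 = 0.5 | 1 − 0.98^25 = 40% |
| 5% | 0.05 × 25 = 1.25 | 1 − 0.95^25 = 72% |
| 10% | 0.10 × 25 = 2.5 | 1 − 0.90^25 = 93% |

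These are children in whom the question arises. Not all of them would be misfiled.

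**The case against.** The strongest reply is that the plan already has several safeguards. Section 9.2.1 names a form for conditions present before placement. Section 5.2 requires good health by vital signs, history and examination. Section 5.3 excludes recent febrile illness (item 1), any condition that could interfere with the study's evaluations (item 7) and vaccination within 7 days either side of enrollment (item 9). A full examination precedes the patch. All of this stands and shrinks the problem. A reader might infer that the plan has no baseline information at all; the documents do not support that. What is absent is a required grade. The form and the examination may note a symptom but need not grade it, and none of the criteria names a mild afebrile one.

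A second reply is that a pre-patch grade would itself be an LAR report, and a noisy one: an infant fussy in clinic is not thereby fussy at home. This stands too, and it shapes the remedy. A reader might infer that unchanged symptoms should be taken out of the reaction table. In an uncontrolled safety study that could hide real reactions on the strength of one day's reading.

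Third, forms are described in the MOP (section 10.2), which is not in the documents and may already include a grade. The gap is therefore shown only for the protocol's visit list and schedule.

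**Conclusion.** The point holds as a cheap improvement: 4 of 5 solicited systemic symptoms have no required pre-patch grade, although the plan's own rules turn on what was there before. Its reach is the descriptive systemic tables after patch 1 and, marginally, attribution of Grade 3 systemic events. Its size is unknown, and it rests on the assumption that the MOP does not already fill the gap.

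Three stronger readings should be resisted. A reader might infer a flaw in the primary analysis, but the application-site endpoint does not use these symptoms. A reader might infer that the tables lack any rule for treatment-emergent events. The term has no formal definition, but section 9.2.1 supplies the substance: collection starts after placement, earlier conditions are excluded and worsening counts. Similarly, the irritability row of Appendix C lacks the baseline qualifier used in 8.1.5, but that is a wording matter. Finally, a reader might infer that the same gap exists before patches 2/3; section 9.4 already covers it.

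**What to change.** Add one item to the pre-application list in 7.1 and to the Day 1 column of Appendix A: the LAR's report, on the Appendix C scale, of irritability, lethargy, appetite and vomiting over the 24 hours before the patch. A 24-hour window is less tied to behaviour in the clinic than a reading at the visit.

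In section 11.3, keep every post-patch solicited systemic symptom in the main table. Beside it, show the number that are new or higher in grade than before the patch. Flag unchanged symptoms; do not remove them. Add no step before patches 2/3.

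The cost is four grades per child, at most 4 × 25 = 100 per cohort, on a short checklist at an existing visit, plus an occasional deferral of Day 1. There is no new visit and no change in sample size. The single-day baseline will be noisy and cannot account for ordinary infant fussiness over the following week.
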